11.5.3.1 Analysis of endpoint

Weight (grams) will be summarized using descriptive statistics for actual and CFB values by visit and treatment group. CFB values will be presented in the summary table in gram units. To obtain CFB in grams, weight (kg) as captured in the eCRF will be multiplied by 1,000.

The same model presented in Section 11.5.2.1 will be used to estimate the difference in mean CFB (in grams) between Bi-26 and Placebo at Day 56, adjusting for baseline weight (grams), age, country, and discharge destination. The adjusted interaction effects (Treatment*Visit) will be presented as estimates of the difference in CFB between treatment groups at each follow-up visit (Day 28, 56, and 90). The associated 95% CIs and p-values will be presented. PROC MIXED will be used for the analysis. Normality will be investigated using q-q plots. If weight is not normally distributed an appropriate transformation, such as the natural log, will be used as outcome for analysis.

A participant listing of weight will be presented with actual values (in kilograms and grams) and CFB (in grams).

The descriptive table, model and listing will be presented for the mITT population. The summary table will be repeated for the PP population.

Confidential Page 34 of 50

Line graphs with the means and 95% CIs for weight (grams) will be presented by treatment group for visits Baseline, 28, 56, and 90.

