8.1. Demographic and Baseline Characteristics

The following information pertaining to the participant will be obtained from the participant's mother at screening:

- Participant's sex, race, ethnicity, date of birth (including day, month, and year), and whether the delivery was a C-section.
- Participant's gestational age in weeks, if known, and the participant's birth weight (in kilograms). This information may be obtained from the hospital medical record if necessary.
- The mother's age will be obtained whenever possible.
- The participant's mother will be asked about breast-feeding practices from the time of the participant's birth, and planned feeding practices during the study (and this information will be captured in the case report form).

A full medical history and full physical examination will be performed at the screening visit (refer to Section 8.3.1). The participant's anthropometric measurements will be taken at the screening visit and at other specified timepoints in the SoA (refer to Table 2 and Section 8.3.1) for more details).

If the eligibility criteria are met, the participant will be enrolled into the study on Day 1. After enrollment, an estimation of socioeconomic status will be obtained if possible.

Hospital discharge to home, or to nutritional rehabilitation unit, will be collected on Day 1 and obtained from either the participant's parent(s)/legal guardian, or the hospital medical record. The anthropometric measurements obtained at Day 1 will be considered baseline for the purposes of statistical analyses (refer to Section 9.2).

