9.7. Primary and Secondary Estimands

Participants randomized to the group receiving 28 days of Bi-26 will be compared to participants randomized to 28 days of placebo for the primary analysis.

Following International Council for Harmonization of Technical Requirements for Pharmaceuticals for Human Use (ICH) E9 (R1) addendum, the estimands relating to the study objectives are constructed by using the 5 following attributes:

- (a) treatment
- (b) population
- (c) variable/endpoint
- (d) population level summary
- (e) intercurrent events.

These attributes were specified to translate the study objective(s) into a treatment effect that is to be estimated (estimand). Refer to Table 4 and Table 5 for a summary of the primary and secondary estimands, respectively.

| Objective | Primary Estimand |
|---------------------------|-------------------------------------------------------------------------------------------------------------------------------------------------------------------------------------|
| To evaluate the change in | a. Population : The mITT population will be used for the analysis. |
| age) of infants receiving | b. Endpoint : WAZ change from baseline (Day 1) to the Day 56 visit in Bi-26 group. |
| B1-20 | c. Population level summary : Mean change from baseline in WAZ in the Bi-26 group compared to placebo with stratification blocking factors and feeding regimen covariate(s). |
| | d. Intercurrent event(s) : Including but not limited to treatment discontinuation. Further details will be specified in the SAP . |

Table 4: Primary Estimands

| Objective | Secondary Estimand | | | | |
|--------------------------------------------------|-------------------------------------------------------------------------------------------------------------------------------------------------------------------------------------------------------|--|--|--|--|
| To evaluate the change in | a. Population : The mITT population will be used for this analysis. | | | | |
| weight of infants receiving Bi-26 | b. Endpoint : weight change (in grams) from baseline (Day 1) to the Day 56 visit in Bi-26 group. | | | | |
| | c. Population level summary : Mean change from baseline in weight in the Bi-26 group compared to placebo with stratification blocking factors and feeding regimen covariate(s). | | | | |
| | d. Intercurrent event(s): Including but not limited to treatment discontinuation. Details will be provided in the SAP. | | | | |

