The weights used to assign the priority of balance to each factor is given by an integer value from 0 to 5 for each of the stratification variables (in this case WAZ, Age, Country, and Discharge destination) as well as for study (overall), stratum and site balance. The same weight is assigned to all levels of the stratification factors. The weights chosen for each of the relevant factors are presented in Table 3. The final choice of weights was also based on the simulations and expert input described above. High priority in balance is given to Study and WAZ as we aim for 1:1 ratio of treatments overall, and within WAZ strata.

The minimization algorithm determines the imbalance scores of assigning the next participant to be randomized to Bi-26 or Placebo. The treatment allocation least likely to cause imbalance based on these scores will be assigned.

The following formula is used to calculate the weighted imbalance score for treatment i:

$$Im_score_i = \sum_{j} w_j Im_{ij}$$

Confidential Page 16 of 50

where w_j is the weight associated with factor j and Im_{ij} is the relative imbalance due to assigning the next participant to be randomized to treatment i. The calculations for the different treatments are done separately, assuming the new participant is randomized to the respective treatment. Given that the target allocation between treatment groups is 1:1, that n participants have been randomized for factor j (in the level of the new participant), that m out of n participants have been assigned to treatment i, the relative imbalance for factor j and treatment i, Im_{ij} , is calculated as

$$Im_{ij} = 2 \times \left| 0.5 - \frac{m+1}{n+1} \right|$$

where

m: # participants already allocated to treatment i in factor j (relevant level)

n: # participants already randomized in factor j (relevant level)

Note that Im_{ij} is calculated assuming the n + 1th participant is randomized to treatment i.

Table 3. Weights Assigned to Factors Used in Dynamic Allocation

Factor	Weight
Study	3
Strata	1
Site	1
WAZ	3
Age	2
Age Country	1
Discharge destination	1

The final algorithm for treatment allocation of a participant is the following:

- 1. Determine the imbalance within factor, Im_{ij} , of assigning the next participant to treatment i, for each factor, given treatment allocations within each factor up to that point
- 2. Draw a random integer, say r_1 , between 0 and 100
- 3. If:

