11.2 Demographics and Baseline Characteristics

Demographics and baseline characteristics will be summarized using descriptive statistics by treatment group and overall. The denominators for percentages will be the number of participants in each treatment group with non-missing data for the variable of interest for the ITT population. The number of participants with missing data at baseline, without percentages, will be displayed for each of the variables. Two participant listings will be presented with treatment group, one for demographic variables and the other for baseline variables as listed below, for the ITT population.

The following demographic and baseline variables will be summarized and listed:

- Country (Bangladesh, Kenya, Pakistan, Tanzania).
- Age (days) at enrollment both numeric and categorical (30-59 days, 60-120 days).
- Sex (Male, Female).
- Race (Asian, Black, Indian, White, Other).
- Ethnicity (Bantu, Bengali, Cushite, Kalenjin, Kikuyu, Luo, Luyha, Nilo-Hamite, Pashtun, Punjabi, Sairiki, San, Sindhi, Other).
- Infant been exposed to HIV (Human immunodeficiency virus) (Yes, No).
- Type of HIV exposure (Hospital, Household, Infected Mother, Other, Unknown).
- Infant HIV status, only positive will be indicated as it will be recorded in the medical history.
- Weight (grams).
- Length (cm).
- Mid-upper arm circumference (MUAC).
- Head circumference (cm).
- Skinfold thickness at the subscapular and triceps (mm).
- Bilateral pedal edema (Yes, No).
- Weight-for-age z-score (WAZ) both numeric and categorical (-3 to -2, \leq -3).
- Weight-for-length z-score (WLZ).
- Birth weight (grams).
- Gestational age (weeks).
- Birth delivery method (C-Section, Vaginal birth).
- Discharge destination (Home, Nutritional Rehabilitation Unit).
- Primary type of feeding the infant has received since birth (Exclusively breastmilk, Formula exclusively, A mix of breastmilk and other types of feedings, Other milk exclusively).
- Antibiotics received within prior 30 days (Yes, No).
- Have refrigerator in house (Yes, No).

Confidential Page 26 of 50

See Section 11.5.1 for the calculation of WAZ, Section 11.6.6 for the calculation of WLZ and the derivations of baseline values of MUAC and head circumference.

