11.5 Efficacy

11.5.1 Calculation of Weight-for-age z-score

WAZ is calculated at Screening and all clinical visits (Days 1, 28, 56, and 90).

The WAZ score is calculated in EDC using the approach defined by the WHO [2]. Given the weight (kg), sex and age (in days) of a participant, the WAZ is calculated as

Confidential Page 31 of 50

$$WAZ = \frac{\left(\left(\frac{Weight}{M}\right)^{L} - 1\right)}{L \times S}$$

where L, M, and S are pre-derived parameter estimates generated by the WHO. L, M, and S are conditional on the Sex and Age (days) of the infant. The lookup tables for the values of L, M, and S can be found on the WHO website [2]. Distinct tables for males and females are given.

WAZ is calculated directly in EDC and need not be derived. WAZ is rounded off to 2 decimals. The value for WAZ (at enrollment) after rounding off is used for randomization and defining the strata $(-3 < \text{WAZ} < -2, \text{WAZ} \le -3)$ (also used for study eligibility).

11.5.2 Primary outcome: CFB in WAZ at Day 56

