11.5.2.1 Analysis of endpoint

WAZ will be summarized using descriptive statistics for actual and CFB values by visit and treatment group.

A MMRM will be used to estimate the difference in mean CFB between Bi-26 and Placebo, adjusting for covariates baseline WAZ, age (in days), country and discharge destination. The model will use CFB in WAZ as outcome and include the following effects:

- Fixed effects: Treatment, Visit (categorical), Treatment*Visit interaction, WAZ at baseline (continuous), Age (in days) at baseline, Country, Discharge destination
- Random intercepts: participant.

and will be fit using data from all planned follow-up visits where WAZ was measured, ie, Day 28, 56, and 90 visits. The adjusted interaction effects (Treatment*Visit) will be presented as estimates of the difference in CFB between treatment groups at each follow-up visit (Day 28, 56, and 90). The associated 95% CIs and p-values will be presented. PROC MIXED will be used to fit the models. SAS code for the models is provided in Appendix 3. If the WAZ score is not normally distributed, an appropriate transformation, such as the natural log, will be used as outcome for analysis. Normality will be investigated using q-q plots.

A participant listing of WAZ will be presented with actual values and CFB.

The descriptive table, model and listing will use the mITT population. The summary table will be repeated for the PP population.

Line graphs with the means and 95% CIs for WAZ will be presented by treatment group for visits Baseline, 28, 56, and 90.

Confidential Page 32 of 50

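### The key secondary model for weight gain in grams has no sex term, although moving from WAZ to grams removes the sex standardisation; a small, free gain in precision is left unused

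*SAP*

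**What the plan says.** The primary model (SAP 11.5.2.1) is a repeated-measures model for change in WAZ at Days 28, 56 and 90, with a random participant intercept. Its terms are "Fixed effects: Treatment, Visit (categorical), Treatment*Visit interaction, WAZ at baseline (continuous), Age (in days) at baseline, Country, Discharge destination". SAP 11.5.3.1 applies the same model to change in grams, "adjusting for baseline weight (grams), age, country, and discharge destination". Neither list contains sex.

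SAP 11.5.1 explains why the WAZ model can manage without it: "L, M, and S are conditional on the Sex and Age (days) of the infant", with separate lookup tables for boys and girls.

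Sex is available. Protocol 8.1 collects at screening "Participant's sex, race, ethnicity, date of birth (including day, month, and year), and whether the delivery was a C-section", and SAP 11.2 summarises sex at baseline. It is not an allocation factor; SAP 7.2.1 names the stratification variables as "in this case WAZ, Age, Country, and Discharge destination". Nor is it among the possible confounders in SAP 11.5.2.4.2 or the named subgroups in SAP 8.2.

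The estimand for this endpoint (Protocol Table 5, SAP Table 2) calls for the stratification blocking factors and feeding covariates, and does not list sex.

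**The concern.** The gram model was carried over from a model in which sex had already been dealt with. In the WAZ analysis, the outcome and the baseline covariate are both measured against sex-specific references. In the gram analysis, neither is.

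Under the SAP's sex-specific tables, a boy and a girl of the same age and the same weight in grams have different WAZ. Baseline grams and age therefore do not fix the infant's nutritional position; baseline grams, age and sex together do. Degree of underweight is the trial's entry criterion and an allocation factor, and sex is the one item needed to bring that information back into the gram model.

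If gain over 56 days differs between boys and girls after allowing for baseline weight and age, that variation stays in the residual. What is at stake is the width of the confidence interval for the only endpoint labelled key secondary, not its validity.

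**Working it through.** **1. The plan's own figure.** Protocol 9.4 and SAP 7.1.3 assume a WAZ difference of 0.45, SD 1.3, two-sided 5% and at least 90% power, and state 177 per group (354 in total). The normal approximation gives 176 per group. The t-based calculation gives power 0.8994 at 176 and 0.9011 at 177, so 177 is reproduced. No effect, SD or power is stated for grams.

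**2. Formula.** Let d be the boy-girl difference in 56-day gain given the other covariates, and SD the residual SD without sex. Take half the infants as boys. The share of residual variance due to sex is R² = 0.25 × d² / SD². Adjusting for sex multiplies the standard error by √(1 − R²) and is worth a factor 1/(1 − R²) in sample size. This treats Day 56 as a simple two-group comparison.

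**3. Numbers.** Both d and SD are assumptions.

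| d (g) | SD (g) | R² | SE smaller by | Sample size factor |
|---|---|---|---|---|
| 100 | 800 | 0.25 × 10,000 / 640,000 = 0.4% | 0.2% | 1.004 |
| 200 | 600 | 0.25 × 40,000 / 360,000 = 2.8% | 1.4% | 1.029 |
| 50 | 1000 | 0.06% | 0.03% | 1.001 |
| 300 | 400 | 14.1% | 7.3% | 1.164 |

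The first two rows bound the mid-range; the last two are the extremes of the wider range tried. On 354 evaluable infants, the mid-range is worth 354 × 0.0039 ≈ 1 to 354 × 0.0286 ≈ 10 infants.

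**4. Power, for scale only.** Suppose the standardised effect in grams equalled that for WAZ (0.45/1.3), which the documents do not say. By the normal approximation, power at 177 per group would rise from 90.3% to between 90.4% and 91.0% in the mid-range, and to 94.0% in the most favourable corner.

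**5. Chance imbalance in sex.** With 177 per group, the SD of the difference in the proportion of boys is √(2 × 0.25/177) = 0.053, so 1.96 SD is about 10 percentage points. Multiplied by d = 100 to 200 g, this moves the difference by about 10 to 21 g. The variance this adds is d² × 2 × 0.25/n, and the total variance of the treatment difference is 2 × SD²/n. Their ratio is 0.25 × d²/SD², which is R² again.

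**The case against.** The strongest reply is that nothing here is wrong. The estimand does not ask for sex, sex is not an allocation factor, and leaving out an optional prognostic covariate breaks no rule in the plan. Birth weight or gestational age could be proposed in the same way. The primary result already gives a sex-standardised comparison of the same weights. All of this is fair, and it keeps the point at the lowest level of importance. It does not remove the case for adding sex: of the covariates one might propose, sex is the one that the change of scale itself took out, and it costs almost nothing.

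A second reply is that the WAZ formula concerns weight level, whereas the endpoint is change, with baseline weight and age already in the model. That stands in part. A reader might infer from SAP 11.5.1 that 56-day gain must differ materially by sex. The section shows only that reference weight at a given age depends on sex; the documents contain no reference values and no sex-specific gains. Eligibility and baseline weight may also absorb part of any difference.

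A third reply concerns chance imbalance. A reader might count it as a second harm beside lost precision. Step 5 of the working shows that it is the same quantity: the unadjusted standard error already allows for it.

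**Conclusion.** The omission is real, and the comparison remains unbiased without sex. The loss is one of precision and is probably small: an SE about 0.2% to 1.4% larger than it need be, under assumed differences of 100 to 200 g and SDs of 600 to 800 g.

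A reader might suppose a larger share, such as 5% of residual variance. By the same formula, d = 2 × SD × √R², so 5% needs a boy-girl difference of about 268 g at SD 600 g, or 358 g at SD 800 g, after adjustment for baseline weight and age. The documents offer nothing to support that.

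One limit remains. SAP 10.1 says that the SAS code is in Appendix 3, but only the summary table is readable in the text available, so the code could not be checked. The written model in 11.5.2.1 and 11.5.3.1 lists no sex term.

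**What to change.** Before unblinding, add sex as a fixed effect to the gram model in SAP 11.5.3.1, align the SAS code with it, and record the addition in SAP section 9, since the estimand's covariate list does not include sex. The cost is one degree of freedom and two short edits, with no new data.

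A sex-by-visit term is a reasonable option. A single sex effect assumes the same boy-girl difference in gain at Days 28, 56 and 90, and the difference may widen with time. The interaction costs two further degrees of freedom. The WAZ model has less need of the term and can stay as it is. The choice should be fixed now, because adding sex after unblinding would look selective.

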11.5.3.2 Subgroup analysis

Summary statistics, including 90% confidence intervals for difference in CFB will be presented by treatment and visit for subgroups as specified in Section 8.2 for weight. The mITT population will be used for this analysis.

11.5.4 Secondary outcome: Change over time in WAZ by duration of dosing

11.5.4.1 Analysis of endpoint

The difference in the change over time will be represented as the estimated difference in CFB at Day 90 using the results generated by the model as described in Section 11.5.2.1 for the PP population.

In order to take duration of dosing into account, the model described above will be adjusted by study intervention compliance (see Section 11.4) and presented in separate tables for the mITT and PP populations.

11.5.5 Secondary outcome: Proportion of infants with increase in WAZ ≥ 0.3 , 0.4 and 0.5 at Day 56

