6.2 Secondary Objectives

Table 2. Secondary Objectives

Objective		Estimand
Key Secondary		
To evaluate the change in weight of	a)	Population : The mITT population will be used for this analysis.
infants receiving Bi-26	b)	Endpoint : weight change (in grams) from baseline (Day 1) to the Day 56 visit in Bi-26 group.
	c)	Population level summary : Mean change from baseline in weight in the Bi-26 group compared to placebo with stratification blocking factors and feeding regimen covariate(s).
	d)	Intercurrent event(s): Including but not limited to treatment discontinuation.
Secondary		
To estimate the treatment response over time associated with Bi-26	a) b)	Population : The mITT population will be used for the analysis. Endpoint : WAZ change from baseline (Day 1) over time through the Day 90 visit (longitudinal assessment) by duration of dosing.
	c)	Population level summary : Mean change from baseline in WAZ over time in the Bi-26 group compared to placebo with stratification blocking factors and feeding regimen covariate(s).
	d)	Intercurrent event(s): Including but not limited to treatment discontinuation.
To assess the proportion of infants	a)	Population : The Safety population will be used for the analysis.
who achieve a specified change in WAZ from baseline to Day 56	re a specified change in b)	Endpoint : Proportion of infants with $a \ge 0.3$, 0.4, and 0.5 change in WAZ from baseline (Day 1) to Day 56 visit.
	c)	Population level summary : Frequency and percentages of infants with a ≥ 0.3 , 0.4, and 0.5 change in WAZ from baseline (Day 1) to Day 56 in the Bi-26 and placebo groups.
	d)	Intercurrent event(s): Including but not limited to treatment discontinuation.

Confidential Page 11 of 50

To assess the proportion of infants who achieve a specified WAZ at Day 56

- a) **Population**: The Safety population will be used for the analysis.
- b) **Endpoint:** Proportion of infants with a WAZ > -2 at Day 56 visit.
- c) **Population level summary:** Frequency and percentages of infants with a WAZ > -2 at Day 56 in the Bi-26 and the placebo groups.
- d) **Intercurrent event(s)**: Including but not limited to treatment discontinuation.

To assess the re-hospitalization rate

- a) **Population**: The Safety population will be used for the analysis.
- b) **Endpoint:** Number of re-hospitalizations for acute non-surgical illness through the Day 56 visit.

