7.1.3 Justification of Sample Size

[figure not shown]
The primary study hypothesis is that the difference in the mean change from baseline in WAZ is larger for participants randomized to at least 28 days of Bi-26 relative to placebo.

For the sample size calculation for the primary hypothesis, it is assumed that the between group difference in the WAZ change from baseline in 0.45 with a standard deviation of 1.3. Based on the above assumption(s) using a 2-sided alpha of 5% and a power of at least 90%, a total of 354 participants, 177 in each group are required.

Confidential Page 14 of 50

Assuming a 10% loss to follow-up and a 3% mortality rate, a sufficient number of participants will be screened to ensure approximately 396 randomly assigned participants are enrolled, 198 in each treatment group.

Figure 2. Sample size sensitivity

N/group, 1-sided $\alpha = 2.5\%$, Power=90%

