8.1.5 Per-Protocol (PP) Population

All participants randomly assigned to study intervention, who received the study intervention, have a Day 90 visit, and did not substantially deviate from the protocol procedures. Important protocol deviations will be evaluated individually by the sponsor to decide whether it has basis to exclude a participant from the PP population. Deviation from study intervention compliance (see Section 11.4) is defined as compliance of less than 80%. Participants will be analyzed according to the intervention they actually received (for details refer to Section 11.1).

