9 CHANGES IN CONDUCT OR PLANNED ANALYSES FROM THE PROTOCOL

- Dynamic randomization will include all stratification variables, including WAZ in determining the treatment allocation.
- Populations for secondary endpoints previously PP, changed to Safety with results to be reported for PP populations as sensitivity analysis.

Confidential Page 21 of 50

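### SAP Table 2 (mITT), Section 9 (Safety) and Section 11.5.4.1 (PP) name different populations for the WAZ-through-Day-90 endpoint, and 11.5.4.1 designates the PP contrast as its result

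*SAP*

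**What the plan says.** The endpoint is WAZ change from baseline over time through Day 90, by duration of dosing. Protocol Table 5 assigned it to the PP population. The SAP then gives three answers:

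- **Table 2 (Section 6.2), estimand for response over time:** "The mITT population will be used for the analysis".
- **Section 9, changes from the protocol:** "Populations for secondary endpoints previously PP, changed to Safety with results to be reported for PP populations as sensitivity analysis". This endpoint was PP in the protocol, so the sentence covers it.
- **Section 11.5.4.1, the section that runs it:** the Day 90 difference is obtained "using the results generated by the model as described in Section 11.5.2.1 for the PP population". To bring in duration of dosing, the model "will be adjusted by study intervention compliance (see Section 11.4) and presented in separate tables for the mITT and PP populations".

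Under Section 8.1.5, PP infants must "have a Day 90 visit, and did not substantially deviate from the protocol procedures". Compliance below 80% counts as a deviation, and infants are grouped by the product they actually received. The mITT population (Section 8.1.4) is every randomised infant with at least a partial dose, grouped as randomised.

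Section 11.5.2.1 fits the same mixed model in mITT and presents treatment differences at Days 28, 56 and 90 with confidence intervals and p-values. Section 11.5.2.4.1 and Table 8 both label the plain PP run of that model a sensitivity analysis.

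**The concern.** Day 90 is the only assessment of whether a weight gain lasts about two months after dosing stops. The section responsible for that result offers two routes. One restricts the comparison to infants who attended Day 90, did not substantially deviate and are grouped by product received. The other adjusts for compliance, which is also observed after randomisation. Neither matches the mITT estimand in Table 2.

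Requiring a Day 90 visit also drops the Day 28 and Day 56 values of infants who died or left, which the mITT mixed model would use. The same PP output is the endpoint result in 11.5.4.1 and a sensitivity analysis in 11.5.2.4.1. Someone following Table 2, Section 9, Section 11.5.4.1 or Table 8 could each report a different Day 90 number as the secondary endpoint.

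**Working it through.** **1. The plan's own figure.** The SAP states a sample size only for the primary comparison: "it is assumed that the between group difference in the WAZ change from baseline in 0.45 with a standard deviation of 1.3", "using a 2-sided alpha of 5% and a power of at least 90" percent, and "a total of 354 participants, 177 in each group are required". Normal formula: n = 2 × (1.960 + 1.282)² × 1.3² / 0.45² = 175.4, so 176 per group. The two-sample t version gives 176.35, so 177. The figure reproduces, with power 0.903 at 177 per group. No sample size or power is stated for the Day 90 endpoint, and naming its population changes no stated figure.

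**2. What the SAP plans for WAZ at Day 90.**

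| Place in SAP | Population | Compliance-adjusted? | Role given |
|---|---|---|---|
| Table 2 | mITT | not mentioned | estimand of this endpoint |
| Section 9 | Safety; PP alongside | not mentioned | PP is sensitivity |
| 11.5.2.1 and Table 8 | mITT | no | primary model, output includes Day 90 |
| 11.5.2.4.1 and Table 8 | PP | no | sensitivity |
| 11.5.4.1, first paragraph | PP | no | result for this endpoint |
| 11.5.4.1, second paragraph, and Table 8 | mITT and PP | yes | in Table 8, secondary/sensitivity |

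The combination that Table 2 calls for, mITT without conditioning on later behaviour, is produced in 11.5.2.1 but is not designated for this endpoint in 11.5.4.1.

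**3. How far apart the populations are.** Safety and mITT have the same membership: randomised with any dose, even partial. They differ only in grouping, so they diverge only if an infant received the wrong product. The contrast that matters is mITT or Safety against PP.

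**4. Comparison with the other former PP endpoints.** For the WAZ-gain thresholds, WAZ above -2 and re-hospitalisation, Table 2 names Safety, and Sections 11.5.5 to 11.5.7 run Safety and PP. Those follow Section 9. Only the longitudinal endpoint conflicts.

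**5. Can a bias be sized?** In one arm, let q be the share excluded and d the excluded infants' mean deficit, in SD units, relative to those kept. The kept mean exceeds the whole-arm mean by q × d × SD. The shift in the Bi-26 minus placebo difference is (q_B × d_B − q_P × d_P) × SD, which is zero when q and d are equal between arms. The documents give no PP fraction and no arm difference in exclusion, so everything below is assumed.

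Suppose there is no true effect, SD is 1.3, and exclusion takes the lowest share q of a normal index correlated ρ with WAZ change. The kept mean is then ρ × 1.3 × λ(q), with λ(q) = φ(z_q)/(1 − q), where z_q is the q-quantile of the standard normal. This gives λ(0.10) = 0.195, λ(0.15) = 0.274, λ(0.16) = 0.290 and λ(0.25) = 0.424.

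| Excluded, Bi-26 / placebo | Shift, ρ = 0.3 | Shift, ρ = 0.5 |
|---|---|---|
| 13% / 13% | 0 | 0 |
| 10% / 16% | 0.39 × (0.195 − 0.290) = -0.04 | 0.65 × (0.195 − 0.290) = -0.06 |
| 15% / 25% | 0.39 × (0.274 − 0.424) = -0.06 | 0.65 × (0.274 − 0.424) = -0.10 |

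The sign reverses if Bi-26 loses more infants. Against the planning difference of 0.45, 0.04 to 0.10 is 0.04/0.45 = 9% to 0.10/0.45 = 22%. These shifts compare PP with a fully observed arm. They are relevant mainly to infants who attend Day 90 but are excluded for compliance or deviations. Infants who died or left have no Day 90 value in mITT either.

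**The case against.** The strongest reply is that little is missing. Section 11.5.2.1 reports an mITT Day 90 difference, grouped as randomised and without compliance adjustment, and Table 8 already calls the plain PP run a sensitivity analysis. PP membership is settled before unblinding (Section 8.1), so it cannot be chosen to suit the result. PP was the protocol's population for this endpoint, so the 11.5.4.1 text may simply have been carried over. The endpoint is one of several secondary ones with no stated power. The compliance-adjusted model is the SAP's only attempt at the duration-of-dosing element, so it has a purpose.

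Most of this stands, and it limits the point. A reader might infer that the trial will report no randomised comparison at Day 90; Section 11.5.2.1 rules that out. A reader might also take the planned 10% loss plus 3% mortality as the size of a PP bias. Those are overall rates, not a difference between arms. Missing efficacy data are not imputed (Section 10.3.3), so for infants lost before Day 90 mITT adds only their recorded earlier values, used through the model.

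What the reply does not remove is the designation. Fixing PP membership while blinded prevents deliberate choice but not selection by attendance and compliance. The existence of the right estimate in another section does not settle which one is the secondary endpoint.

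**Conclusion.** The population conflict is real and can be read directly from the text. Section 11.5.4.1 designates a Day 90 result that depends on attendance, compliance and product received, against the SAP's own Table 2 estimand and against its own labelling of the PP run elsewhere. That conclusion needs no assumption about size.

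The size of any bias cannot be derived from the documents. It is zero with equal exclusions and deficits; the 0.04 to 0.10 WAZ range rests wholly on assumed unequal exclusion, on ρ of 0.3 to 0.5, and on carrying the planning SD of 1.3 over to Day 90. The primary Day 56 analysis and the sample size are unaffected. The correction should still be made, because it decides which number is reported as persistence of effect.

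**What to change.** Amend the SAP before unblinding:

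1. **Section 11.5.4.1, first paragraph:** replace PP with mITT, so that the Day 90 difference from the 11.5.2.1 model, shown with Days 28 and 56, is the main result for this endpoint.
2. **Plain PP run:** label it sensitivity here too, as 11.5.2.4.1 and Table 8 already do.
3. **Compliance-adjusted model:** keep it, described as supportive for the duration-of-dosing element.
4. **Section 9:** list this endpoint's change as PP to mITT, separately from the endpoints that moved to Safety.
5. **Table 8:** add a row identifying the mITT Day 90 contrast as this secondary analysis.

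The cost is SAP wording and table labels. The estimate is already generated, and neither data collection nor sample size changes.
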